Statistical Analysis	
Randomization: 120 patients will be recruited into the study and randomized to either 0.50 mg/kg Relteceimod or placebo in a 1:1 ratio. Randomization will be performed within site and according to two stratification variables.
 
• Acuity of AKI: whether or not AKI is diagnosed at time of presentation of abdominal infection or surgical confirmation of NSTI; or during the 48 hours following the suspected diagnosis of abdominal infection or surgical confirmation of NSTI.• Subject Age: ≥ 18 to ≤ 75 or > 75 to ≤ 85 years old. 
Four computer generated, blocked randomization lists will be provided for each site, one for each of four strata defined on the basis of the 2 by 2 cross-tabulation of the two stratification variables. Within each block, half of the assignments will be to active drug and half to placebo, in random order. Block sizes will be varied.
 
Blinding: The study will remain blinded as to treatment allocation. The actual randomized treatment allocations will be kept by a contracted third-party responsible only for managing the randomization process. A variable indicating the blinded treatment allocations will not be part of the clinical study data to be managed by the data management clinical research organization (CRO). Therefore, only blinded study data will be available to the primary study statistician and responsible primary programming staff.
 
Analysis Sets:
 
• The intent-to-treat (ITT) analysis set will include all randomized patients.• The As-Treated (AT) analysis set will include all randomized patients who were exposed to study medication (active or placebo). The AT analysis set will be used in the primary safety analyses with patients assigned to actual treatment received.• The modified intent-to-treat (mITT) analysis will include all randomized patients who were exposed to study medication (active or placebo) and had a definitive diagnosis of abdominal sepsis or NSTI with patients assigned to their intended randomized assignment. The mITT set will be used in primary effectiveness comparisons.• Supporting effectiveness analyses may be performed using a Per Protocol (PP) analysis set. 
Primary Analysis: The primary efficacy comparison involves testing the following superiority hypotheses: H₀: $\pi_{0.50} - \pi_{\text{Placebo}} \leq 0$ vs H_a: $\pi_{0.50} - \pi_{\text{Placebo}} > 0$; where $\pi_{0.50}$ and π_{Placebo} represent the true probability of freedom from durable loss of eGFR (alive, free of dialysis, and less than a 37% loss of eGFR (measured with the MDRD formula from the patient's reference eGFR)) at Day 28. Each probability represents the proportion of subjects on each arm expected to achieve freedom from durable loss of renal function. These hypotheses will be tested using an unadjusted chi-square test at a one-sided type 1 error rate of $\alpha=0.025$. The null hypothesis will only be rejected if the proportion of responders is larger in the active drug group compared to placebo.
 
Sample Size Justification: This trial will enroll 120 subjects that will be randomized in a ratio of 1:1 to either Relteceimod 0.50 mg/kg (n=60) or placebo (n=60), each in addition to SoC. Sample size analysis was performed assuming that all patients will be evaluable for the primary endpoint using last observation carried forward (LOCF) for patients missing a serum creatinine value on Day 28.

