-----------------------------	--

	
The primary efficacy hypothesis will be tested using an unadjusted χ^2 statistic with a one-sided $\alpha=0.025$ significance level. The null hypothesis will only be rejected if the investigational drug demonstrates superiority. Statistical power was computed for a range of expected treatment group differences supported by the results of preliminary studies. Based on preliminary data, a total of 120 patients will be enrolled. This sample size results in 89% power if the true success rates are 75% and 50% for the investigational drug and placebo, respectively.
 
Sample Size Re-Estimation: A “Promising Zone” sample size re-estimation interim analysis is planned for when between 50% and 67% of the initial sample size is evaluable for the primary efficacy endpoint⁵³). The purpose of the sample size re-estimation is to maintain (conditional) power when the treatment group difference is smaller than 0.25, but still clinically meaningful.
 
A pre-specified maximum sample size expansion will be specified prior to providing unblinded results to the independent data monitoring committee (iDMC) but in no case will the sample size expansion exceed an additional 200 subjects. With this restriction, only clinically meaningful treatment effects are detectable with good statistical power at the maximum sample size. The specific rules for determining if sample size expansion is permissible and if so, by how much, will ensure control of type 1 error.
 
Specifically, the sample size will be increased up to the maximum to maintain conditional power to as close to 80% as possible, but only if conditional power at the interim analysis is above a pre-specified threshold that results in control of type 1 error to the desired nominal value. If conditional power falls within the Promising Zone, increasing the sample size up to the pre-specified maximum is at the discretion of the Sponsor.
 
Futility Analysis: In addition to sample size re-estimation, a non-binding futility analysis will be conducted at the time of the interim analysis. If conditional power is below a pre-specified futility threshold, enrollment may be immediately stopped at the discretion of the Sponsor.
 
Independent Data Monitoring Committee (iDMC): A detailed iDMC charter will be provided to clarify all relevant issues relating to the conduct of the sample size re-estimation and futility analysis, including specific details regarding the operational procedures with fire-walls to protect against potential operational biases, decision rules, composition of the iDMC members and their conflict of interest statements.
 
Adjudication Committee for Evaluation of AKI Stage and Recovery: Experts chosen for the AKI Adjudication Committee will be independent of the Sponsor and neither they nor their institutions participated in the sample collection or sample measurement studies. Each adjudicator will be provided a form for each patient containing all relevant clinical information. Adjudicators will be blinded to group assignment and clinical data will be identified only by anonymized identification number. Adjudicators will indicate their assessment of AKI staging and recovery independently without consultation with each other. The basis for the adjudication will be the KDIGO consensus criteria corresponding to Stages 1-3 (mild to severe). A two thirds majority was predefined for use as the final adjudication.
 
Secondary Endpoints: Secondary endpoints have been specified from several domains including a similar endpoint but defined at Day 14. Additional secondary endpoints include time to the primary endpoint, AKI free days, SOFA over time, and critical care and hospital stay parameters (hospital length of stay (LOS), ICU and ICU-free days, ventilator days and –free days, vasopressor days and –free

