Table 6 provides a simple evaluation of how the size of maximum sample expansion relates to statistical power for detecting various clinical effect sizes. Table 6 compares statistical power for fixed sample designs with total sample sizes of 120 (the initially planned sample size), 180 (allowing up to 60 more subjects), and 320 (allowing up to 200 more subjects). The selected maximum will be no larger than 200 additional subjects. As noted above, a fixed sample size design randomizing 120 subjects achieves 81.6% power if the treatment group difference is 25% (i.e., 75% versus 50%). Similarly, a fixed sample size design with 180 subjects achieves 82.7% power if the treatment group difference is 21% (i.e., 71% versus 50%). Finally, a fixed sample size design with 320 subjects achieves 82.9% power if the treatment group difference is 16% (i.e., 66% versus 50%). A 16% treatment group difference is still considered clinically meaningful. Therefore, even if a maximum increase of 200 is selected, the study will only have large statistical power to detect clinically meaningful treatment effects.

Additionally, the lower bounds of the Promising Zone when the IA for SSR is performed with 67% of the initially planned sample size is 0.39 when the maximum increase is 60 subjects; but is reduced to 0.31 when the maximum increase is set to 200. If the observed proportions of responders are 0.66 (0.65) and 0.50 for active and placebo subjects, respectively, conditional power will be 0.3905 (0.3148). Therefore, in any case, the observed treatment group differences will need to be larger than about 0.15 depending on the scenario, for any sample size expansion to be even allowed under the Promising Zone approach. This makes it unlikely that the treatment group difference will be found to be statistically significant unless the true treatment effect exceeds about 0.15.

Table 6: Examples of power for fixed sample design (1-sided $\alpha=0.025$)

Control	Reltecimod	Power (N=120)	Power (N=180)	Power (N=320)
0.5	0.60	0.194	0.269	0.435
0.5	0.61	0.226	0.316	0.508
0.5	0.62	0.261	0.367	0.581
0.5	0.63	0.299	0.420	0.651
0.5	0.64	0.339	0.475	0.717
0.5	0.65	0.382	0.530	0.777
0.5	0.66	0.426	0.586	0.829
0.5	0.67	0.472	0.641	0.874
0.5	0.68	0.518	0.693	0.909
0.5	0.69	0.565	0.742	0.937
0.5	0.70	0.611	0.787	0.958
0.5	0.71	0.656	0.827	0.973
0.5	0.72	0.700	0.863	0.983
0.5	0.73	0.741	0.894	0.990
0.5	0.74	0.780	0.919	0.994
0.5	0.75	0.816	0.940	0.997

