12.9 Analysis of Other Covariate Effects

Covariates will be assessed for potential confounding (due to lack of perfect randomization balance) or effect modification (subgroup efficacy heterogeneity) using multiple logistic regression. Covariates will include but are not limited to age, race, sex, site, and clinical severity scores at baseline. Other baseline variables in which randomization failed to produce adequate balance between groups will be examined in supporting analyses. This will be done through stratified analyses and/or multiple logistic regression. Covariate effects on estimates and interactions will be assessed to see if there is evidence of efficacy heterogeneity. Results from all subgroups analyses will be considered hypothesis-generating.

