2.1 Primary Efficacy Analysis

2.1.1 Primary Superiority Hypothesis

The primary effectiveness endpoint is *freedom from durable loss of renal function at Day 28*. Success requires:

- Alive at Day 28,
- Free of dialysis at Day 28, and
- Less than a 37% loss of estimated Glomerular Filtration Rate (eGFR; measured with the Modification of Diet in Renal Disease (MDRD) formula from the patient's reference eGFR) at Day 28.

Reference creatinine values, baseline AKI stage and percentage loss of eGFR will be determined through algorithmic determination (see details below). Percentage loss of eGFR determined algorithmically will be based on a comparison of eGFR at screening compared to an algorithmically determined reference creatinine value.

The primary efficacy comparison involves testing the following one-sided superiority hypotheses: **H₀: $\pi_{0.50} - \pi_{\text{placebo}} \leq 0$ vs H_a: $\pi_{0.50} - \pi_{\text{placebo}} > 0$** ; where $\pi_{0.50}$ and π_{placebo} represent the true probability of freedom from durable loss of renal function at Day 28. Each probability represents the proportion of subjects on each arm expected to achieve complete recovery. These hypotheses will be tested using a one-sided type 1 error rate of $\alpha=0.05$. The null hypothesis will only be rejected if the investigational drug demonstrates superiority. An unadjusted chi-square test will be used to test this hypothesis.

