5.3 Secondary Endpoints

The same analysis as described above will be performed for freedom from durable loss of renal function at Days 14 and 90 and from improvement for freedom from durable loss of renal function as Days 14, 28, and 90.

Additional secondary endpoints include mSOFA over time, critical care and hospital stay parameters (ICU and ICU-free days, ventilator days and –free days, vasopressor days and –free days, and hospital length of stay (LOS)). Analyses for these endpoints will generally be descriptive, with emphasis on characterizing clinical effect sizes. Nominal p-values will be presented. Categorical outcomes will be described using counts and percentages with nominal p-values determined through chi-square or exact methods. Critical care and hospital stay endpoints will be described using non-parametric approaches including using concordance statistics to characterize clinical effect sizes and Wilcoxon rank sum tests to determine nominal statistical significance. Methods appropriate for time-to-event endpoints including survival and life-table methods will be used for time-to-recovery endpoints.

5.4 mSOFA

The Sequential Organ Failure Assessment score or SOFA was originally developed to track a patient's status during a stay in an intensive care unit (ICU)^{4,5}. Each of six organ systems are evaluated and assigned ordinal scores from 0 to 4. A total score is the sum of the component scores. For this study, the liver component is excluded from the sum score and the resulting sum score is referred to in this study as 'mSOFA'.

Several approaches will be taken to summarize changes over time and between treatment groups in the clinical scores as described below. Special handling of mSOFA scores includes the following:

1. If an individual organ score is missing but other scores for that day are non-missing, the organ systems that were not evaluated are assumed to be free of organ failure and given a value of zero when determining the sum score.
2. If all organ scores are missing for a specific day, the mSOFA total score from that day will be imputed using LOCF with the following exception, LOCF will not be performed after patient death.
3. When summarizing the individual organ scores apart from the mSOFA total scores, the same rules as above will apply.

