7.1 Site Specific Numbers of Patients by Analysis Set

Table 14.1.1.1 summarizes the numbers of patients screened and for each analysis set by site.

Table 14.1.1.2 summarizes the numbers of patients by site, analysis set, and treatment group.

Table 14.1.1.3 summarizes the numbers of patients by site, treatment group, and randomization stratum in the mITT Analysis set. The primary efficacy analyses will be performed in the mITT analysis set.

Randomization strata are defined as follows:

- **Acuity of AKI:** whether or not AKI is diagnosed at time of presentation of abdominal infection or during the 48 hours following the suspected diagnosis of abdominal infection.
- **Subject Age :** ≥ 18 to ≤ 75 or > 75 to ≤ 85 years old.

Table 14.1.1.4 provides the same summary for the As Treated (primary Safety) analysis set.

Table 14.1.1.5 provides the same summary for the PP (secondary efficacy analysis set).

Totals across all sites will be provided for these tables.

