8.1 Primary AKI Endpoint

The numbers and percentages of patients in each group meeting the primary efficacy endpoint of complete recovery (*freedom from durable loss of renal function at Day 28*) is summarized in Table 14.2.1.1 for the mITT (primary efficacy) analysis set. This table also includes the statistical significance of this endpoint based on an unadjusted chi-square statistic. Study success requires one-sided $p \leq 0.05$ for this endpoint which is equivalent to a two-sided $p \leq 0.10$ as long as the percentage of subjects achieving the endpoint is larger in the actively treated group compared to placebo. This table also provides the estimated treatment group difference and 90% confidence interval corresponding to the one-sided significance level. The lower bound of the 90% confidence interval is equivalent to the lower bound of a 1-sided 95% confidence interval. Based on the study data, it can be concluded that the true difference in success rates is at least equal to the lower bound of the 1-sided 95% confidence intervals. Table 14.2.1.1 also provide the same summaries for the components of the primary endpoint.

- Alive at Day 28,
- Free of dialysis at Day 28, and
- Less than a 37% loss of estimated Glomerular Filtration Rate (eGFR; measured with the Modification of Diet in Renal Disease (MDRD) formula from the patient's reference eGFR) at Day 28.

Table 14.2.1.2, and 14.2.1.3 repeat these analyses in the AT and PP analysis sets, respectively.

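### Randomisation is stratified by AKI acuity and age, but the primary test is an unadjusted chi-square and no fixed analysis by the randomisation strata is planned

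*SAP*

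**What the plan says.** Protocol 12.6.1 and SAP 2.2 randomise within site, with four lists per site formed by crossing AKI acuity (present at presentation, or diagnosed in the next 48 hours) with age (up to 75, or over 75). SAP 2.2 sets block sizes at 2 or 4. The protocol synopsis plans up to 90 sites for 120 patients.

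The primary test uses neither factor. SAP 2.1.1 and 5.2: "An unadjusted chi-square test will be used to test this hypothesis". SAP 8.1: the result in Table 14.2.1.1 is "based on an unadjusted chi-square statistic". Protocol synopsis: "These hypotheses will be tested using an unadjusted chi-square test", and under sample size, "The primary efficacy hypothesis will be tested using an unadjusted" chi-square statistic. Protocol 12.5.1 and 12.5.2 and SAP 2.1.2 say the same. SAP 5.3 carries the choice over: "The same analysis as described above will be performed for freedom from durable loss of renal function at Days 14 and 90".

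The factors do appear elsewhere. SAP 5.6 lists both as subgroups. On counts by stratum, SAP 7.1 says: "Table 14.1.1.3 summarizes the numbers of patients by site, treatment group, and randomization stratum in the mITT Analysis set". SAP 7.2 tabulates baseline balance. SAP 5.7 assesses covariates, taken from the subgroup list, by Mantel-Haenszel analysis, logistic regression or both. Protocol 12.9 says: "Covariates will include but are not limited to age, race, sex, site, and clinical severity scores at baseline". AKI acuity is not named there.

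**The concern.** When a trial stratifies its randomisation on factors thought to matter, the analysis would normally use them. Here blocking cannot be relied on to balance them. At 90 sites there are 90 × 4 = 360 site-by-stratum cells for 120 patients, so most blocks stay incomplete.

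If the arms differ on a prognostic factor, the unadjusted comparison carries that difference into the primary result. A success could then be challenged as owing to the imbalance, or a real effect could be missed. The plan has no single pre-specified stratified result to settle the question. SAP 5.7 leaves the method open, and its covariate list includes Day 14 mSOFA, which is measured after randomisation and may be affected by treatment.

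**Working it through.** **1. The plan's power figures.** Inputs: 60 per arm, 75% v 50%, no continuity correction (SAP 2.1.2; protocol Table 6).
- Null SE = √(2 × 0.625 × 0.375 / 60) = 0.0884. Alternative SE = √((0.25 + 0.1875) / 60) = 0.0854.
- One-sided 0.05: Φ((0.25 − 1.645 × 0.0884) / 0.0854) = Φ(1.225) = 0.890, as in SAP Table 1.
- One-sided 0.025: Φ((0.25 − 1.960 × 0.0884) / 0.0854) = Φ(0.899) = 0.816, as in protocol Table 6.
- The synopsis gives 89% at 0.025. That does not reproduce and is a separate error.

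**2. How often acuity is imbalanced.** The documents do not give patients per site or stratum shares. The simulations assume equal sites and base shares of 45/30/15/10% (40% in one acuity group, 25% over 75), with 20,000 trials per scenario. Acuity favours active by more than 10 points in 10.5, 8.0, 4.3 and 1.3% of trials with 90, 40, 20 and 10 sites, and favours placebo about as often.

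**3. Size of the effect by hand.** Suppose no treatment effect, 50% success, and an odds ratio (OR) of 2 for acuity.
- Difference in success between acuity groups ≈ 0.25 × ln 2 = 0.173.
- A 10-point imbalance shifts the arm difference by 0.10 × 0.173 = 0.0173.
- SE = √(2 × 0.25 / 60) = 0.0913, so the shift is 0.19 SE.
- Error at nominal 0.05: 1 − Φ(1.645 − 0.19) = 0.073 if active is favoured, and 1 − Φ(1.645 + 0.19) = 0.033 if placebo is.
- The same steps with OR 1.5 (0.25 × 0.405 = 0.101; shift 0.11 SE) give 0.063 and 0.040.

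This is a rough check at exactly 10 points. Trials beyond that threshold are more imbalanced.

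**4. Simulated error in trials with acuity imbalance over 10 points** (nominal one-sided 0.05, same OR for both factors, 20 to 90 sites; OR 1.5 at base shares only):

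| OR per factor | Unadjusted, active favoured | Unadjusted, placebo favoured |
|---|---|---|
| 1.5 | 0.063–0.066 | 0.032–0.041 |
| 2 | 0.073–0.086 | 0.023–0.032 |
| 3 | 0.087–0.101 | 0.017–0.022 |

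The stratified test stays at about 0.045 to 0.055. Over all trials both tests hold their size: 0.044 to 0.052 unadjusted, 0.049 to 0.051 CMH.

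**5. Power, CMH minus unadjusted, in points at 75% v 50%:**

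| OR per factor | One-sided 0.05 | One-sided 0.025 |
|---|---|---|
| 1 | −1.0 to −0.3 | −1.3 to −0.4 |
| 1.5 | −0.4 to 0.0 | −0.7 to −0.1 |
| 2 | −0.2 to +0.6 | −0.1 to +1.0 |
| 3 | +1.0 to +2.1 | +1.6 to +3.0 |

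At OR 1 and 70% v 50%, the loss reaches 1.3 points at 0.05 (72.5% to 71.2%) and about 1.7 points at 0.025. A continuity-corrected CMH would lose 4.6 to 5.1 points (0.05) or 6.3 to 6.9 points (0.025) at OR 1 and 75% v 50%, so the test must be uncorrected.

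**6. Interim analysis.** Protocol 12.5.3 says "conditional power will be 0.3905 (0.3148)" for 66% (65%) v 50%. These figures reproduce from raw proportions with 40 per arm. For 66%: z = 0.16 / √((0.2244 + 0.25) / 40) = 1.469; 1.469 / √(2/3) = 1.799; Φ((1.799 − 1.960) / √(1/3)) = 0.390. They rest on the unadjusted statistic.

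Size with an unadjusted interim at 80 of 120, maxima of 180 or 320, and one-sided 0.025 was 0.0227 to 0.0246 with a CMH final test, against 0.0220 to 0.0255 with an unadjusted final test. Other settings were not checked.

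**The case against.** The strongest reply is that nothing is broken. The unadjusted test is pre-specified consistently in both documents, matches the power tables and tests the stated hypothesis directly. This stands. A reader might infer that ignoring the strata inflates the type I error. It does not: the two directions of imbalance average out, and with imbalance within 10 points the unadjusted error is 0.048 to 0.052 for OR up to 2.

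Second, the harm rests on assumed prognostic strength and on thin sites. This also stands. At OR 1 to 1.5 the stratified test loses a little power or breaks even, and large imbalance is uncommon if recruitment is concentrated in 10 to 20 sites.

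Third, SAP 5.6, 5.7, 7.1 and 7.2 already use the factors, so it would be wrong to say that the plan ignores them. It is also fair that protocol 12.9 does not close its list and that the SAP prevails. But SAP 5.7 does not commit to one method, ties nothing to the primary decision, and draws on a list containing a post-randomisation variable. Naming one stratified sensitivity analysis there would close part of the gap, but would leave the deciding test exposed.

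Finally, protocol 12.5.1 values a conventional statistic, but the reason it gives is to avoid weighting patients by when they were randomised. CMH does not do that either.

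**Conclusion.** The point holds as an improvement to the analysis, not as a validity error. The benefit is an error rate near nominal whichever way chance imbalance falls in the single trial run, plus some power if the factors are prognostic.

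Its size depends on three things the documents do not give: prognostic strength, stratum shares and patients per site. The simulations also assume that both factors are equally prognostic and that sites are equal in size. A reader might take 1.3 points as a cap on the power cost. It applies only at 75% v 50%; smaller effects at one-sided 0.025 cost up to about 1.7.

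**What to change.** - **Primary test.** Use a CMH test without continuity correction over the four acuity-by-age strata (not site). Apply it at the governing one-sided alpha once the SAP's 0.05 and the protocol's 0.025 are reconciled.
- **Stratum source.** Take strata from the randomisation system. SAP 2.2 and 7.1 word acuity for abdominal infection only, while protocol 12.6.1 adds NSTI.
- **Estimate.** Report the Mantel-Haenszel risk difference with a named variance estimator and the matching interval: 90% for 0.05, 95% for 0.025.
- **Sparse strata.** No collapse rule is essential. A stratum with one arm empty adds zero to both the CMH numerator and its variance, so the test can still be computed.
- **Unadjusted chi-square.** Keep it as a fixed sensitivity analysis, for the subgroup repeats of Table 14.2.1.1 (SAP 5.6, 8.8), and for the interim promising-zone calculation.
- **SAP 5.7.** Limit covariates to baseline variables.
- **Interim.** Confirm type I error for the timing, maximum and alpha finally chosen; protocol 12.5.3 allows 50 to 67% information and up to 200 extra patients.

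The cost is wording in SAP 2.1.1, 2.1.2, 5.2 and 8.1 and in protocol 12.5.1, 12.5.2 and the synopsis. SAP 5.3 needs a sentence saying whether the Day 14 and Day 90 analyses follow. A note should say that the power tables and conditional-power figures rest on the unadjusted test. All this should be settled before unblinding, when SAP 1 requires the SAP to be final. The statistical cost is the small power loss in step 5 if neither factor is prognostic.
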